12.4. Exploratory Endpoints

12.4.1. Markers of Immune Reactivity to Immunoradiation

Markers of immune reactivity will be prospectively measured in lung tumor resection specimens, draining lymph nodes (DLNs) and serial peripheral blood samples from 16 stage III NSCLC patients who receive 3 doses of preoperative immunotherapy concurrently with thoracic radiation, prior to planned surgery. All samples will be analyzed using whole exome sequencing, multicolor flow cytometry, immunohistochemistry +/- multicolor IF for candidate surrogate markers of immune response to

18-Nov-2020 Page **118** of **164**

IND #134339

immunoradiation, including frequency of coordinate expression of co-regulatory molecules by peripheral blood lymphocytes, tumor infiltrating lymphocytes, DLN cells and tumor cells. PD-L1, CD3, CD4, CD8, granzyme B, CD20, and CD56 staining will be performed on biopsy and resection specimen and frequency of expression tabulated. Additional molecules may be assessed as well.

12.4.2. Analysis of Exploratory Endpoints

These exploratory analyses will be descriptive/graphical in nature, and are designed to generate new hypotheses to be tested in future clinical studies. When parameters of immune response are measured, continuous variables will be summarized with means and standard deviations. Dichotomous and categorical variables will be summarized using proportions with exact 95% confidence intervals and counts, respectively. These summaries will be computed for each treated patient at multiple time points before and after immunotherapy administration as indicated in the study schema. Plots will be used to show the changes in immune response over time both for each individual. For each patient, comparisons in the pre and post-durvalumab (cohort 1) or durvalumab+tremelimumab (cohort 2) responses will be compared using paired t-tests (or Wilcoxon signed rank tests if appropriate) for continuous variables and McNemar's test for dichotomous or categorical variables. Associations between immune responses will be explored graphically (e.g. scatterplots, boxplots) and numerically (e.g. correlations, $\chi 2$ tests). Similar comparisons will be performed between immunoradiation-treated patients, and control patients with stage III resectable NSCLC who do not receive immunoradiation, but are enrolled on a companion tissue collection protocol

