8.6. Biomarker Evaluation methods [step]

8.6.1. **Immunohistochemistry**

We will discern phenotypes of immune cell populations in tumor and lymph node biopsy and resection tissue using immunohistochemistry, including but not limited to: CD3, CD4, CD8, CD25, CD45RO, CD56, CD20, CD68, granzyme B, FOXP3, TIM-3, LAG3, TIGIT, PVR-Ig, PD-1, PD-L1, eomesodermin, Tbet, phosphor-S6K and Egr2 (anergy marker) using validated commercially available or locally-developed antibodies to evaluate changes in the immune composition of the tumor microenvironment. Pathologists will assign an intratumoral and peritumoral immune cell infiltrate grade of (0) none, (1) rare lymphocytes (2) focal lymphohistocytic aggregates or (3) severe diffuse infiltration⁸⁶. Pathologists will designate 3 representative fields to be evaluated by image analysis, which will allow for the data to be reported as a percentage of area with positive staining. These studies will provide a comprehensive view of cellular subsets and immune checkpoint molecule expression in tumors from untreated patients and how cellular subsets and key immune regulatory molecules are impacted intratumorally after treatment with anti-PD-L1+/- CTLA-4 and thoracic radiation. PD-L1 expression in FFPE specimens will be assessed as detailed below.

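### Section 12.4.2 gives McNemar's test to multi-level paired markers, so the ordered 0-3 infiltrate grade has no suitable pre/post test and a shift in grade may be missed

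*Combined protocol and SAP*

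**What the plan says.** Section 12.4.2 (Analysis of Exploratory Endpoints) sets the pre/post tests by type of variable. Continuous markers are "compared using paired t-tests (or Wilcoxon signed rank tests if appropriate) for continuous variables". The rest get "McNemar's test for dichotomous or categorical variables". The same section summarises dichotomous variables by proportions and categorical ones by counts, so it treats them as two kinds of variable, and categorical must include markers with more than two levels.

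Section 8.6.1 (Immunohistochemistry) contains such a marker. Pathologists assign an "immune cell infiltrate grade of (0) none, (1) rare lymphocytes (2) focal lymphohistocytic aggregates or (3) severe diffuse infiltration", as part of a programme to characterise "phenotypes of immune cell populations in tumor and lymph node biopsy and resection tissue using immunohistochemistry". The grade is therefore ordered, has four levels, and can be read both before and after treatment.

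Section 12.4.1 describes samples "from 16 stage III NSCLC patients who receive 3 doses of preoperative immunotherapy", which caps the number of pairs at 16 in a cohort. Section 12.4.2 states no significance level, power, cut-point for a graded marker, or extension of McNemar's test. On controls it adds: "Similar comparisons will be performed between immunoradiation-treated patients, and control patients with stage III resectable NSCLC who do not receive immunoradiation". It names no test for that comparison.

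**The concern.** McNemar's test compares the two kinds of discordant pair in a 2x2 table. A four-level grade gives a 4x4 table, so the stated rule cannot be carried out without a further choice. One choice is to split the grade into low and high. Every patient who moves within the low or the high group then counts as unchanged, and the split could be chosen after the data are seen. The other is Bowker's symmetry test, which keeps four categories but treats them as unordered and spreads the evidence over as many as six cell pairs.

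A general rise of one grade is the kind of change an infiltrate score would be expected to show, and both choices handle it poorly. With at most 16 pairs there is little information to spare. The exploratory objective in section 2.3 asks about changes in immune reactivity before and after immunoradiation, and section 12.4.2 says the results are meant to produce hypotheses for later trials. A missed shift would weaken that use.

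**Working it through.** The plan states no figure for these tests, so there is nothing to reproduce. The calculations below are illustrations.

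**Inputs from the documents:** four ordered grades, 0-3 (section 8.6.1); at most 16 pairs (section 12.4.1); McNemar for categorical and signed-rank for continuous markers (section 12.4.2). **Assumed:** two-sided 5%, all 16 pairs available, and the grade distributions given below.

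**1. A worked example with no power model.** Four patients move 0 to 1, four move 1 to 2, four move 2 to 3, and four do not change.
- Exact signed-rank: 12 non-zero differences, all +1 and all tied. Two-sided p = 2 x (1/2)^12 = 0.0005.
- Exact McNemar: at each of the cuts >=1, >=2 and >=3, only the four patients who cross that cut are discordant, all in one direction. p = 2 x (1/2)^4 = 0.125 at every cut. Five one-way discordant pairs would give 2 x (1/2)^5 = 0.0625 and six would give 2 x (1/2)^6 = 0.031, so at least six are needed for p < 0.05.
- Bowker: three occupied cell pairs, each contributing (4 - 0)^2 / (4 + 0) = 4, for a statistic of 12. p = 0.007 if only the three occupied pairs are counted (3 df), and 0.062 with the full 4 x 3 / 2 = 6 df.

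**2. Power, latent-normal model.** Paired normal scores are cut at -0.67, 0 and 0.67 into grades 0-3, and the post-treatment score is shifted by 0.8 or 1.0 SD. There were 4,000 simulated trials of 16 pairs per setting. The two figures in each cell are for the two shifts.

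| Pre/post correlation | Exact signed-rank | Exact McNemar, best single cut |
|---|---|---|
| 0.3 | 54-74% | 28-47% |
| 0.5 | 65-83% | 31-53% |
| 0.7 | 79-92% | 33-58% |

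At correlation 0.5 the separate McNemar cuts give 7-10% (>=1), 29-44% (>=2) and 31-53% (>=3). With no shift, both tests reject well below 5% of the time, so the signed-rank advantage does not come from a loose test. A repeat simulation agreed within about a percentage point.

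**3. Power, a different model.** Baseline grades 0/1/2/3 in 25/40/25/10% of patients; one-grade rise in 50, 60 or 70%; one-grade fall in 10%; 3,000 simulated trials.
- Signed-rank: 45, 60 and 76%.
- McNemar at its best cut (>=2): 6, 12 and 20%; at the other two cuts, at most 4%.
- Bowker: 27, 42 and 57% if df counts only occupied cell pairs; 0.3, 1 and 6% with 6 df.

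The direction is the same in both models. The size is not.

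**The case against.** The strongest reply is that section 12.4.2 declares these analyses descriptive and hypothesis-generating. No error rate or decision depends on them, and counts and individual plots over time are already planned, so a shift in grades would be visible whatever the test gave. That stands, and it keeps the point small. It does not make the named test suitable, because the section goes beyond description and names significance tests.

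Second, Bowker's test is often regarded as McNemar's test for more than two categories, and some software runs it under that name. So it would be too strong to say that the grade must be collapsed. But the extension is not named, it ignores ordering, and with so few pairs its result depends heavily on the degrees-of-freedom convention.

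Third, the scope is narrow. Section 8.6.1 also reports staining as a percentage of area, which the paired t or signed-rank test covers, and section 12.4.1 does not list the infiltrate grade by name. That also stands: the point concerns graded readouts only.

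A reader might go further and infer from the sentence on controls that the plan applies paired tests to unpaired control patients. The text does not support that. It says the comparisons will be similar and names no test, and the sentence just before it offers "correlations, $\chi 2$ tests" as examples for associations between immune responses; a chi-square test needs no pairing. What remains is missing detail: no independent-group test is named for the controls, who come from a companion tissue protocol. Section 8.6.2 speaks of stage-matched untreated tissue for the RNA work, but that does not create individual pairs.

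**Conclusion.** The concern holds for paired ordered grades. Section 12.4.2 sends the 0-3 infiltrate grade to a two-level test, gives no cut-point or extension, and limits the suitable test to continuous markers. A shift in grade may therefore be missed; it is not bound to be.

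In the worked example the gap is p = 0.0005 against 0.125, given only that pattern of changes. The power figures, about 65-83% against at most about 31-53% at correlation 0.5, rest on an assumed grade distribution, shift, correlation and 5% level, none of which the plan states. The alternative model shows that the size of the loss can differ considerably while its direction stays the same.

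The comparison with controls is under-specified, which calls for a clarifying sentence and no more. The importance is low: the endpoints are exploratory, and the primary safety and feasibility analyses, which are proportions with exact binomial intervals, are untouched.

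**What to change.** In section 12.4.2:

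1. Restrict McNemar's test, in its exact form, to two-level markers.
2. Compare paired ordered grades, including the 0-3 infiltrate grade, with the exact Wilcoxon signed-rank test across patients, using one value per patient and tissue location and mid-ranks for ties. If a marker has several unordered categories, name Bowker or Stuart-Maxwell explicitly. If a low/high split of a grade is wanted as well, fix the cut-point before the data are seen.
3. As a minor clarification, state that comparisons with the companion-protocol controls use independent-group tests: two-sample t or Wilcoxon rank-sum for continuous and ordered markers, and Fisher's exact or chi-square for categorical ones.

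The cost is a few lines of text, with no new patients, samples or procedures. The one added assumption is that differences between grades can be ranked, which is mild for a four-level ordered score.

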12.5. Patient Accrual

The accrual rate for this study is expected to be 1-2 patients per month. It is estimated that JHH sees between 25-35 patients with stage III resectable NSCLC per year that would be suitable for enrollment onto this study. For each cohort, it is projected to complete full accrual within 2 years if the experimental regimen is tolerable and feasible.

13. Ethical and Regulatory Requirements

13.1. Ethical conduct of the study

The study will be performed in accordance with ethical principles that have their origin in the Declaration of Helsinki and are consistent with ICH/Good Clinical Practice, and applicable regulatory requirements Subject data protection.

13.2. Ethics and Regulatory Review

Institutional Review Board Information regarding study conduct and progress will be reported to the Johns Hopkins Institutional Review Board (IRB).

The Protocol Chair is responsible for performing the following tasks:

18-Nov-2020 Page **119** of **164**

- Coordinating, developing, submitting, and obtaining approval for the protocol as well as its subsequent amendments.
- Assuring that the correct version of the protocol is used.
- Taking responsibility for the overall conduct of the study and for monitoring the progress of the study.
- Reviewing and ensuring reporting of Serious Adverse Events (SAE).
- Reviewing data from all sites.

13.3. Informed consent

An investigator will explain to each subject the nature of the study, its purpose, procedures involved, expected duration, potential risks and benefits. Each subject will be informed that participation in the study is voluntary and that she may withdraw from the study at any time, and that withdrawal of consent will not affect her subsequent medical treatment. This informed consent will be given by means of a standard written statement and will be submitted for IRB approval prior to use. No patient will enter the study before her informed consent has been obtained. In accordance with the Health Information Portability and Accountability Act (HIPAA), the written informed consent document (or a separate document to be given in conjunction with the consent document) will include a subject authorization to release medical information to the study sponsor and supporting agencies and/or allow these bodies, a regulatory authority, or Institutional Review Board access to subjects' medical information that includes all hospital records relevant to the study, including subjects' medical history.

13.4. Changes to the protocol and informed consent form

Any changes to the protocol or informed consent form will be made in the form of an amendment and must be approved by the IRB before implementation. The Principal Investigator is responsible for the coordination and development of all protocol amendments.

14. Study Management

14.1. Training of study site personnel

Study staff at the Sidney Kimmel Comprehensive Cancer Center Upper Aerodigestive Division will be trained in the details of this protocol and accompanying protocol materials prior to commencement of this study. Standard instructional materials will be supplied to study staff at a site initiation visit. Details of biospecimen acquisition, workflow and processing will be detailed in the study lab manual. Details of the study agents will be available in the study pharmacy manual.

18-Nov-2020 Page **120** of **164**

14.2. Monitoring of the study

Evaluation of safety will be monitored continuously through day 90 following the last dose of study therapy or 30 days post surgery, whoever comes first. The evaluations will be conducted under the direction of [name], [name], and the study statistician; additional information may be found in the statistical section.

14.3. Study timetable and end of study

We conservatively estimate accrual of 1-2 patients every month. Accounting for an Approximate 10% drop-out rate, we estimate a target accrual of 40 patients in 20-24 months (cohorts 1 and 2). Additional study sites have been identified will contribute to accrual, if needed.

15. Data Management

Eligible patients will be entered on study centrally at the Sidney Kimmel Comprehensive Cancer Center at the Johns Hopkins University by the CROCC Lead Study Coordinator. All sites should email the CRO Coordinating Center at [contact] as well as the Lead CROCC Study Coordinator. The Registration Form, and Eligibility Worksheet will be supplied to each participating site.

If a patient does not receive protocol therapy following registration, the patient's registration on the study may be canceled. The Coordinating Center should be notified of cancellations as soon as possible.

All sties must maintain the electronic case report forms in the Clinical Research Management System (CRMS). All data must be entered into the CRMS eCRFs within 2 weeks of the visit dates. For participating sites, de-identified source documents must be uploaded into CRMS.

At the time of registration:

- Registration Form
- Informed Consent Form (signed by the subject)
- Eligibility Checklist
- Source documents related to eligibility and randomization

Within 2 weeks after registration:

- Baseline study case report forms
- Pertinent source documents

Within 2 weeks after final dose of study medication:

- On study case report forms
- Pertinent source documents

18-Nov-2020 Page **121** of **164**

IND #134339

The Study Coordinator at the participating site will then e-mail ([contact] and the CROCC Lead Study Coordinator) to verify eligibility. To complete the registration process, the CRO Coordinating Center will:

- Assign a patient study number
- Register the patient on the treatment portion of the study
- Email the patient study number to the participating site
- Email the research nurse or data manager at the participating site

The investigator will permit study-related monitoring, audits, and inspections by the IRB, government regulatory bodies, and University compliance and quality assurance groups of all study related documents. The investigator will ensure the capability for inspections of applicable study-related facilities (e.g. pharmacy, diagnostic laboratory, etc.).

The SKCCC Compliance Monitoring Program will provide external monitoring for JHU-affiliated sites in accordance with SKCCC DSMP (Version 6.0, 02/21/2019). The SMC Subcommittee will determine the level of patient safety risk and level/frequency of monitoring.

The PI is responsible for internally monitoring the study and establishing additional external data & safety monitoring oversight, as required. The PI will also monitor the progress of the trial, review safety reports, and confirm that the safety outcomes and response assessments favor continuation of the study.

Data monitoring of this protocol will occur on a quarterly or annual at minimum basis with the frequency dependent on the rate of subject accrual and the progress of the study. The protocol will be monitored internally (Johns Hopkins East Baltimore and Bayview Medical Center Campuses) at SKCCC by the Principal Investigator and externally by the SKCCC CRO QA in accordance with SKCCC guidelines. Trial monitoring and reporting will be done through the Safety Monitoring Committee (SMC) at SKCCC. The Johns Hopkins SKCCC CRO Coordinating Center will be responsible for data monitoring at AHN and any other participating sites.

Interim analysis of toxicity, outcome, and ongoing scientific investigations will be performed every 6 months by the Sidney Kimmel Comprehensive Cancer Center Data Safety Monitoring Board (SKCCC DSMB). The SKCCC DSMB will review aspects of this trial that are outlined in the responsibilities section of the Data and Safety Monitoring Board (DSMB) Guidance. If the committee decides that amendments should be made to this trial, recommendations will be made in writing to the Study Principal Investigator. The study team will submit modifications to the IRB within 60 days of receipt from the DSMB. The Associate Director of Clinical Research, will arbitrate any disagreements between the DSMB and the study Principal Investigator. These changes may include early termination of accrual if deemed appropriate.

18-Nov-2020 Page **122** of **164**

15.1. Meetings

Teleconferences of all investigators, research nurses and other study staff involved in the study will take place, starting once both sites have enrolled a subject. The following study team members involved with the conduct of the trial will be included as appropriate: study coordinators, data managers, research nurses, sub-investigators, collaborators (if applicable), and statistician. During these meetings matters related to the following will be discussed: enrollment rate relative to expectation, characteristics of participants, retention of participants, adherence to protocol (potential or real protocol violations), validity and integrity of the data, toxicities, acquisition of serum samples and transfer to lab, and progress of data for objectives.

15.2. Study governance and oversight

The safety of all AstraZeneca clinical studies is closely monitored on an ongoing basis by AstraZeneca representatives in consultation with Patient Safety. Issues identified will be addressed; for instance, this could involve amendments to the study protocol and letters to Investigators.

15.3. Multicenter Guidelines

Protocol Chair

- The Protocol Chair is responsible for performing the following tasks:
- Coordinating, developing, submitting, and obtaining approval for the protocol
- as well as its subsequent amendments
- Assuring that all participating institutions are using the correct version of the protocol.
- Taking responsibility for the overall conduct of the study at all participating institutions and for monitoring the progress of the study.
- Reviewing and ensuring reporting of Serious Adverse Events (SAE)
- Reviewing data from all sites

Coordinating Center

The Coordinating Center is responsible for performing the following tasks:

- Ensuring that IRB approval has been obtained at each participating site prior to the first
 patient registration at that site, and maintaining copies of IRB approvals from each site.
- Managing central patient registration.
- Collecting and compiling data from each site.
- Establishing procedures for documentation, reporting, and submitting of AE's and SAE's to the Protocol Chair, and all applicable parties.
- Facilitating audits by securing selected source documents and research records from participating sites for audit, or by auditing at participating sites.

18-Nov-2020 Page **123** of **164**

Participating Sites

Participating sites are responsible for performing the following tasks:

- Following the protocol as written, and the guidelines of Good Clinical Practice (GCP).
- Submitting data to the Coordinating Center via CRMS eCRFs.
- Providing redacted source documentation.
- Registering all patients with the Coordinating Center by submitting patient registration form, and signed informed consent promptly.
- Providing sufficient experienced clinical and administrative staff and adequate facilities and equipment to conduct a collaborative trial according to the protocol.
- Maintaining regulatory binders on site and providing copies of all required documents to the Coordinating Center.

16. Investigational Product and Other Treatments

16.1. Identity of investigational product(s)

TABLE 11. LIST OF INVESTIGATIONAL PRODUCTS FOR THIS STUDY

Investigational product	Dosage form and strength	Manufacturer
Durvalumab	50 mg/mL solution for infusion after dilution	MedImmune
Tremelimumab	20 mg/mL solution for infusion after dilution	MedImmune

